6.2. Study Schedule of Activities

Assessments	Screening	Consent	Before Receipt of Test Product	Test Product Received	Event 1	15 Minutes After Event Start	30 Minutes After Event Start	60 Minutes After Event Start
Study Window								
Screening Survey	X							
Consent		X						
Baseline Survey			X					
Demographics			X					
Acknowledgement of receipt of test product				X				
Symptom Diary					X			X
4-point Likert Scale					X	X	X	X
Test Product Consumed					X			
Medications & Supplements			X					
AE Assessment					X	X	X	X
Study Exit Survey								

Assessments	Event 2	15 Minutes After Event Start	30 Minutes After Event Start	60 Minutes After Event Start	Event 3	15 Minutes After Event Start	30 Minutes After Event Start	60 Minutes After Event Start	Study Exit
Study Window									
Screening Survey									
Consent									
Baseline Survey									
Demographics									
Acknowledgement of Receipt of Test Product									
Symptom Diary	X			X	X			X	
4-point Likert Scale	X	X	X	X	X	X	X	X	
Test Product Consumed	X				X				
Medications & Supplements									
AE Assessment	X	X	X	X	X	X	X	X	X
Study Exit Survey									X

6.3. Participant Enrollment and Follow-Up

Participants suffering from mild to moderate symptoms of indigestion and heartburn will complete a cloud-based, HIPAA-secured screening survey to determine eligibility. All eligibility criteria must be met for participants to be approved for enrollment in the study. Participants will be provided informed consent and the opportunity to ask questions related to the study procedures, risks and benefits, and rights related to participation in the study. Participants who sign the study informed consent will be prospectively enrolled in the study and provided a link to a patient portal, which provides study resources. Participants will take the study formula at the onset of symptoms and provide information related to symptoms of indigestion/heartburn during the follow-up period. A remote study coordinator may prompt participants to provide study information to ensure that the study forms are completed. Efforts will be taken to ensure minimal withdrawals and loss to follow-up.

6.4. Adverse Event and Safety Monitoring

Adverse Events (AEs) are defined as any untoward medical occurrences described by the study participant. All AEs will be self-reported and documented on the platform. The AEs will be reviewed by the study team including the remote trial coordinator and study principal investigator and reported according to the IRB requirements. Participants who experience adverse events will be advised to seek medical attention.

In the event that a participant experiences an adverse event, the clinical study manager or clinical ops coordinator will notify both the PI and Sponsor. The Sponsor will take appropriate action according to their standard operating procedures for any adverse events that warrant action by the sponsor.

6.4.1. Anticipated Adverse Events

Anticipated Adverse Events are complications that are known to be associated with the test product (in high doses exceeding recommended use):

- Headache
- Amenorrhea
- Upset Stomach
- Diarrhea
- Hives
- · Difficulty breathing
- Facial swelling
- Drowsiness
- Tiredness

Vomiting

6.4.2. Adverse Event Relationship

Each reported AE will be assessed by the Investigator for relatedness, severity and causality.

6.4.3. Serious Adverse Events

A Serious Adverse Event is an Adverse Event that leads to death or to serious deterioration in the health of the participant that either resulted in a life-threatening illness or injury, or a permanent impairment of a body structure or body function.

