7.1. Study Outcomes Measures

Analysis populations:

The *intent to treat* (ITT) population consists of all participants who are consented, report the onset of indigestion and heartburn, and have taken the study medication at least once. The primary analysis will be in the ITT population.

Primary Endpoint:

The primary endpoint has two components, reduction in indigestion severity and reduction in heartburn severity. Participants will be asked to rate each symptom (bloating, early fullness during a meal, pain or discomfort in the upper abdomen, burning in the upper abdomen, pain/burning in the center of your chest, nausea, vomiting, burping) on a 4-point Likert scale at 4 time points: prior to taking the test product, 15, 30, and 60 minutes after taking the test product. The improvement in symptoms from baseline will be evaluated on a pairwise basis separately for each component and each time point. P-values will be computed for the improvement.

There is no control group for the primary analysis.

Secondary Endpoints:

Secondary endpoints will be gathered on the subjective experience of these participants related to general health, personal experience with the test product. The secondary endpoints will be self-reported by the participant on their online portal. There will be a questionnaire related to general health and the subjective experience of the participant administered at baseline and at study exit.

The purpose of the secondary analyses is to investigate the association between various baseline and other measurements and outcomes. These secondary analyses are considered hypothesis generating, and the descriptions are somewhat informal. The trial data may suggest secondary analyses not described here.

Secondary endpoints:

- The time to other intervention will be analyzed.
- A longitudinal analysis will be performed for participants who report on more than one incident of heartburn or indigestion.
- Adverse events will be summarized.
- An additional data presentation will consist of results from both Treatment and Control
 in similar studies appearing in the literature. There will be no formal statistical
 comparison of results from this study and historical studies.
- The Net Promoter Score will be summarized and compared against outcomes.
- Comparison against normal behavior will use the paired sample t-test.

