13.1.7. Appendix G Adverse Event Form

Upset Stomach AE document

- 1. Did you experience any side effects after taking the test product? Y/N
 - a. If so, did you experience any of the following
 - o itching, rash, hives, throat/lip/tongue swelling, wheezing
 - low blood pressure, fainting, chest pain, shortness of breath, palpitations, irregular heart beat
 - o severe, persistent nausea, vomiting, diarrhea, or abdominal pain
 - o difficulty urinating, decreased urination
 - o fatigue, appetite loss, yellowing skin/eyes, itching, dark urine
 - severe joint/muscle pain
 - o slurred speech, one-sided weakness of face, arm, leg, vision
 - o abnormal bleeding from nose or gums
 - o blood in urine, stool, vomit,
 - o marked mood, cognitive, or behavioral changes, thoughts of suicide
 - o Other:
- 2. Please give a description of the event
- 3. How soon after taking the test product did you experience the side effect?
- 4. What did you do to alleviate the side effect?
- 5. Did you have to go to the hospital or see a doctor for this side effect?
 - a. Please describe any diagnosis or treatment that they provided.
 - b. If you were seen in the hospital, please upload any discharge paperwork or other documents from the hospital.

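### Under section 6.4.3 an adverse event that led to hospital admission with full recovery would not be classed as serious, although Appendix G asks about hospital attendance and requests discharge papers

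*Combined protocol and SAP*

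**What the plan says.** Section 6.4.3 of the protocol defines seriousness in one sentence. It opens "A Serious Adverse Event is an Adverse Event that leads to death or to serious deterioration in the health of the participant" and continues "that either resulted in a life-threatening illness or injury, or a permanent impairment of a body structure or body function". No other section that I could find adds a criterion.

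Appendix G, the participant's adverse event form, asks "Did you have to go to the hospital or see a doctor for this side effect". It then asks for any diagnosis or treatment, and adds: "If you were seen in the hospital, please upload any discharge paperwork or other documents from the hospital".

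Three passages govern what happens next:

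- Section 6.4: "The AEs will be reviewed by the study team including the remote trial coordinator and study principal investigator and reported according to the IRB requirements". It also has the investigator and the sponsor notified when a participant has an adverse event.
- Section 6.4.2: "Each reported AE will be assessed by the Investigator for relatedness, severity and causality".
- Section 7.1: "Adverse events will be summarized". This is the only safety analysis stated.

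**The concern.** The trial asks participants for evidence of hospital care and then gives that evidence no part in deciding whether an event is serious. The definition turns on death, threat to life and permanent impairment. The investigator's listed tasks do not include judging seriousness at all.

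What is at stake is the classification. The study is remote and self-reported, and section 11 acknowledges that symptoms get no medical review. Hospital paperwork is the only third-party medical record that the forms request. If a report states that there were no serious adverse events, a reader will probably take it that nobody was admitted for one. Under section 6.4.3 as written, that inference would be unsafe.

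**Working it through.** The plan states no figure on this point, so there is none to reproduce. The check is to apply the definition to each kind of outcome, follow an admission through the plan, and then size one case.

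**Step 1: apply section 6.4.3.** The restricting clause attaches to the deterioration in health, and its either/or form leaves no residual category.

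| Outcome of the adverse event | Criterion met in 6.4.3 | Class |
|---|---|---|
| Death | First | Serious |
| Life-threatening, admitted or not | Second | Serious |
| Permanent impairment, admitted or not | Third | Serious |
| Admitted, not life-threatening, full recovery | None | Not serious |

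Only the last row is affected.

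**Step 2: follow the last row through the plan.**

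- Appendix G: the participant answers yes to the hospital-or-doctor question, describes the treatment and is asked to upload papers.
- Section 6.4: the investigator and the sponsor are notified, the study team reviews the event, and it is reported as the IRB requires.
- Section 6.4.2: relatedness, severity and causality are assessed. Seriousness is not listed, and no rule refers to the hospital answer.
- Section 7.1: the event enters the adverse event summary.

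The event is therefore handled at each stage, but at no stage does the admission make it serious.

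**Step 3: check what the form captures.** The main question pools a hospital visit with a doctor visit. The follow-up concerns anyone seen in hospital, which need not mean admitted. There is no admission field, so admission would have to be inferred from free text or from uploaded papers.

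**Step 4: size, for illustration only.** The documents give no admission rate, so no expected number can be derived. Suppose exactly one such event. Section 5.1 gives a desired 97 treated participants, and section 7.3 calls for exact intervals for discrete variables.

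- Not classed as serious: 0/97 = 0%. The exact 95% upper limit is 1 − 0.025^(1/97) = 3.7%.
- Classed as serious: 1/97 = 1.0%, with an exact 95% interval of 0.03% to 5.6%.
- If 200 participants were treated instead: 0/200 has an upper limit of 1.8%, and 1/200 = 0.5% has an upper limit of 2.8%.

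**The case against.** The strongest reply is that little is lost. The event reaches the investigator and the sponsor, is reviewed, is reported under the IRB's rules and is summarised. Section 2.2.3 adds routine review by the investigator in line with regulatory and GCP guidelines. A form may also collect hospital details to inform severity and causality without making them a test of seriousness, so the two passages do not strictly contradict each other.

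Most of this stands, and it rules out several stronger readings:

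- A reader might infer that such admissions would be missed. They would not: they would be recorded and reviewed as adverse events. Only the serious label is absent.
- A reader might infer that a planned serious-event rate would be biased. The documents plan no such rate or table, and 97 is a power-based target rather than a safety denominator.
- A reader might infer that admission data are already in hand. The pooled question does not isolate admission.
- A reader might infer from entries such as "Facial swelling" in section 6.4.1 that admissions are to be expected. That list is tied to doses above recommended use, and a life-threatening reaction would already meet the definition.

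Two parts of the reply do not dispose of the point. The general references to GCP do not amend an explicit definition, which is what study staff would apply. And assessing severity is not the same as classifying seriousness, which section 6.4.3 defines separately by outcome.

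**Conclusion.** The point holds as a gap in classification. Followed exactly, the protocol would class an adverse event that led to admission and full recovery as non-serious, even with the discharge papers on file.

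The size is unknown. The 1.0% shows what one case among 97 would amount to. It is not an estimate of how often this would happen, and the treated number may differ from 97.

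The conclusion assumes that section 6.4.3 is applied as written and that no other study document widens it. That admission ought to count as serious is a judgement about sound safety reporting. It is not derived here from guidance outside the documents. The change is worth making because the rule is explicit, the study has few other independent sources of medical information, and the correction is cheap.

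**What to change.** Reconcile sections 6.4.2 and 6.4.3 with Appendix G:

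- **Section 6.4.3:** add hospital admission to the definition of a serious adverse event.
- **Section 6.4.2:** add seriousness to what the investigator assesses for each event.
- **Appendix G:** split the pooled question into three items: saw a doctor, was seen in hospital, was admitted to hospital.
- **Portal:** flag only a hospital answer for assessment of seriousness. A doctor visit should not trigger the flag, because section 6.4 itself advises participants with adverse events to seek medical attention.

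The cost is one phrase in 6.4.3, one word in 6.4.2, a small form change and a portal flag. The reported count of serious events may rise. The primary analysis and the sample size are not affected.

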6.5. Lost to Follow-Up

If a participant fails to provide event information via the study/patient portal 30 days after the start of the trial, the remote coordinator will attempt to contact the participant to ascertain whether or not the participant has had an episode of indigestion or heartburn or not and if the participant wishes to and/or should continue in the study.

Before a participant is deemed lost to follow up, the investigator or designee must make every effort to regain contact with the participant (where possible, 3 telephone calls and, if necessary, a certified letter to the participant's last known mailing address or local equivalent methods). These contact attempts should be documented in the participant's study record.

Should the participant continue to be unreachable, he/she will be considered to have withdrawn from the study and the study exit form will be completed.

6.6. Test Product Packaging/Handling/Storage/Accountability

- The 3-episode supply of test product will be packaged and labeled with ingredients and a study ID number.
- Participants will receive guidance on how to report receipt, store, and use the test product.
- Hawthorne Effect Inc. will support storage and shipment of test product, documentation of test product assignment, and completion of test product accountability.

6.7. Study Management

This study uses a decentralized clinical trial format to foster inclusivity, diversity and accessibility for a broad study population and to ensure efficiencies for enrollment and study data collection. The study will be managed using an end to end virtual clinical trial platform called Hawthorne Effect Study Visit Management Platform which is designed to make patient participation in clinical trials more accessible and as least burdensome as possible. The Hawthorne Effect platform (www.hawthorne-effect.com) is GCP/ICH/21CFR and HIPAA compliant. Hawthorne Effect uses a network of specialty vetted and trained healthcare professionals, or HEROs who are study

investigators, screeners and conduct personalized patient visits for screening and follow-up. For this trial, the Hawthorne Effect study visits will be virtual, and the platform will be used to collect patient reported outcomes and to track screening, enrollment and study compliance.

7. Statistical Considerations

7.1. Study Outcomes Measures

Analysis populations:

The *intent to treat* (ITT) population consists of all participants who are consented, report the onset of indigestion and heartburn, and have taken the study medication at least once. The primary analysis will be in the ITT population.

Primary Endpoint:

The primary endpoint has two components, reduction in indigestion severity and reduction in heartburn severity. Participants will be asked to rate each symptom (bloating, early fullness during a meal, pain or discomfort in the upper abdomen, burning in the upper abdomen, pain/burning in the center of your chest, nausea, vomiting, burping) on a 4-point Likert scale at 4 time points: prior to taking the test product, 15, 30, and 60 minutes after taking the test product. The improvement in symptoms from baseline will be evaluated on a pairwise basis separately for each component and each time point. P-values will be computed for the improvement.

There is no control group for the primary analysis.

Secondary Endpoints:

Secondary endpoints will be gathered on the subjective experience of these participants related to general health, personal experience with the test product. The secondary endpoints will be self-reported by the participant on their online portal. There will be a questionnaire related to general health and the subjective experience of the participant administered at baseline and at study exit.

The purpose of the secondary analyses is to investigate the association between various baseline and other measurements and outcomes. These secondary analyses are considered hypothesis generating, and the descriptions are somewhat informal. The trial data may suggest secondary analyses not described here.

Secondary endpoints:

- The time to other intervention will be analyzed.
- A longitudinal analysis will be performed for participants who report on more than one incident of heartburn or indigestion.
- Adverse events will be summarized.
- An additional data presentation will consist of results from both Treatment and Control
 in similar studies appearing in the literature. There will be no formal statistical
 comparison of results from this study and historical studies.
- The Net Promoter Score will be summarized and compared against outcomes.
- Comparison against normal behavior will use the paired sample t-test.

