Objectives: The purpose of this study is to demonstrate whether this plant-based

remedy will reduce the severity of symptoms of occasional indigestion and heartburn. This trial will gather data on performance of the test product. These data will be used to describe the performance currently,

and potentially to design a two-arm trial in the future

Primary Endpoints:

• The primary endpoint is reduction in indigestion severity and reduction in heartburn severity. There is no control group for the primary analysis.

Secondary Endpoints:

- The time to other intervention will be analyzed.
- A longitudinal analysis will be performed for participants who report on more than one incident of heartburn or indigestion.
- Adverse events will be summarized.
- An additional data presentation will consist of results from both Treatment and Control in similar studies appearing in the literature. There will be no formal statistical comparison of results from this study and historical studies.
- The Net Promoter Score will be summarized and compared against outcomes.
- Comparison against normal behavior will use the paired sample t-test

Table OF Contents

1.	KEY	ROLES	
2.	Back	kground Information and Scientific Rationale	
		Background Information	
2	2.2.	Scientific Rationale	10
	2.2.1.	. Potential Risk	10
	222	Known Potential Benefits	11

3. Study Objectives	12

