2.1. Background Information

The primary hypothesis of the present study is that supplementation with the Upset Stomach Relief test product will reduce the severity of the symptoms of occasional indigestion and heartburn.

Dyspepsia, also known as indigestion, is a common symptom with an extensive differential diagnosis and a heterogeneous pathophysiology. It occurs in approximately 25 percent of the population each year, but most affected people do not seek medical care. Approximately 25 percent of patients with dyspepsia have an underlying organic cause. However, up to 75 percent of patients have functional (idiopathic or non-ulcer) dyspepsia with no underlying cause on diagnostic evaluation. Patients with functional dyspepsia usually describe postprandial fullness, early satiety, and/or epigastric pain/burning. Symptoms may be severe enough to limit usual activities. Some patients may have nausea, vomiting, or heartburn; however, these symptoms are usually infrequent. [28] The most common approach to treat occasional indigestion and heartburn is to use antacids to neutralize what is often believed to be an overproduction of stomach acid. This acidblocking approach can perpetuate the problem when used over a long period of time. Acid blocking also has the drawback of causing deficiencies in certain vitamins and minerals over time, such as calcium. By interfering with the digestive process, an overgrowth of bacteria and imbalances in gut health can also worsen health states. The Upset Stomach Relief test product is an herbal solution with ingredients that may ease occasional indigestion and heartburn, while helping to strengthen the digestive tract over time. [4]

There are several causes of indigestion. Acid accumulation and improper gastrointestinal emptying can both prompt dyspepsia. Additionally, stomach or intestinal ulcers formed by bacteria named *Helicobacter pylori* can result in infection that ultimately will cause indigestion. Other potential causes can be from the intake of over-the-counter medications, like ibuprofen, overeating, fatty, greasy, or spicy food, alcohol, and caffeine. [5]

While dietary and lifestyle changes can ease the symptoms of indigestion and heartburn, HLNatural, Inc. created the test product to reduce occasional indigestion and heartburn. The test product is a plant-based remedy formulated with ingredients that have demonstrated

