2.2.3. Minimization of Risks

Research participants will be carefully screened to meet enrollment criteria. Participants meeting exclusion criteria will not be enrolled. The study participant informed consent will be presented with clear description of the study requirements and opportunity to have questions answered before enrollment. Once an event occurs, review of symptoms will be ascertained at onset, 15, 30, and 60 minutes. Reporting of adverse events will be reviewed routinely and in accordance with regulatory guidelines (21CFR, GCP) by the Principal Investigator. Participants with occurrence of worsening symptoms or adverse

events will be advised to stop taking the test product, may seek medical attention, and exit the study.

3. Study Objectives

The purpose of the present study is to evaluate 1) the impact of the test product on symptoms of occasional indigestion and heartburn in 200 adult participants who suffer from occasional indigestion and heartburn and 2) the subjective experience of these participants related to general health, indigestion and heartburn symptoms, and personal experience with the test product.

This will be evaluated based on the primary and secondary endpoints. These endpoints, the analysis populations, and their respective measures are described below. Further details on the methods for measuring the outcomes can be found in the Study Outcome Measures and Analysis Plan sections.

Primary Endpoint:

The primary endpoint has two components, reduction in indigestion severity and reduction in heartburn severity. Participants will be asked to rate each symptom (bloating, early fullness during a meal, pain or discomfort in the upper abdomen, burning in the upper abdomen, pain/burning in the center of your chest, nausea, vomiting, and burping) on a 4-point scale at 4 time points: prior to taking the test product, 15, 30, and 60 minutes after taking the test product. The improvement in symptoms from baseline will be evaluated on a pairwise basis separately for each component and each time point. P-values will be computed for the improvement. Given that indigestion can impact an individual's quality of life, the primary endpoint was chosen to see the test product's effects on symptoms. [1, 9, 12]

Secondary Endpoint:

Secondary endpoints will be analyzed to evaluate safety and patient satisfaction with relief of symptoms. These include:

- The time to other intervention will be analyzed.

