7.2. Sample Size Considerations

Based on information from a variety of studies a highly pessimistic assumption is that there would be a mean improvement of 0.5 with a standard deviation of 1.5. (These values refer to the 4-point scale.) Based on these assumptions, a sample size of 97 participants would result in a 90% power to detect an improvement using the paired-sample t-test. If data from multiple incidents per participant are useful, the power to detect an improvement would increase. The final sample size of 200 participants has been chosen to allow for various contingencies, including uncertainties about compliance in this self-reported trial, and the fact that some participants may not experience heartburn or indigestion during the trial period.

It should be emphasized that these assumptions are for sample size purposes only. Trial analysis will use the data as collected.

As discussed above, the number 200 may be increased based on observed data concerning the number of participants with indigestion and heartburn. The actual outcomes of treated participants will not be considered in this analysis, merely whether or not enrolled participants have reported starting using the test product. The method of reevaluating the sample size will be described in the Statistical Analysis Plan.

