7.3. Analysis Plan

Separate tables will be presented showing the changes from baseline for each component and each time point. The changes will be evaluated by the paired sample t-test. A longitudinal analysis will be performed for participants who report on more than one incident of heartburn or indigestion.

General statistical methods:

Data will be analyzed using standard statistical methods, as further specified in a statistical analysis plan (SAP), which will be prepared in detail later.

- Data analysis will largely consist of summary statistics and graphs. The only formal group comparisons will be in covariate analyses.
- For continuous variables data presentation will consist of means, confidence intervals computed using the *t*-statistic, medians, and interquartile ranges. Group comparisons will use *t*-tests or ANOVA.
- For discrete variables confidence intervals will use the exact intervals, where available. Group comparisons will use Fisher's exact test, with the Monte Carlo version used where computationally necessary.
- For time to event variables analysis will use the Kaplan-Meier algorithm, and group comparisons will use the log-rank or proportional hazards methods, depending on the data type.
- Visual analog scale values will be treated as continuous variables. Frequency counts will also be provided for scales with 10 or fewer distinct response levels.
- Covariate analyses will investigate the relation between baseline and outcome variables, using methods appropriate to the data types involved. Age, gender, and baseline medications will be included in these analyses where appropriate data are available.
- Present intention is that the analysis will be performed in R, and the precise form of algorithms will be the default of R. Kaplan-Meier, log-rank, and proportional hazards algorithms will be the defaults of the survival package.

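### The primary analysis produces six paired t-tests with no stated alpha, primary time point, multiplicity control or success rule, so the 90% power applies to one test and not to the primary conclusion.

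*Combined protocol and SAP*

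**What the plan says.** The synopsis puts the two components in one sentence: "The primary endpoint is reduction in indigestion severity and reduction in heartburn severity". Section 3 and section 7.1 then separate them: "The improvement in symptoms from baseline will be evaluated on a pairwise basis separately for each component and each time point". They add: "P-values will be computed for the improvement". Eight symptoms are rated on a 4-point scale before dosing and at 15, 30 and 60 minutes. The protocol does not say how those eight ratings form an indigestion score and a heartburn score.

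Section 7.3 names the paired t-test and says: "Separate tables will be presented showing the changes from baseline for each component and each time point". Section 7.2 assumes a mean improvement of 0.5 with SD 1.5 and concludes that "a sample size of 97 participants would result in a 90% power to detect an improvement using the paired-sample t-test". It does not say which component, which time point or which significance level this refers to.

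On purpose, section 2.1 is confirmatory in form: "The primary hypothesis of the present study is that supplementation with the Upset Stomach Relief test product will reduce the severity of the symptoms". The synopsis objectives are partly descriptive: "These data will be used to describe the performance currently". Further methods are left to a later document: "as further specified in a statistical analysis plan (SAP), which will be prepared in detail later".

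**The concern.** Two components at three time points make six primary p-values. The protocol does not say what pattern of them would support the primary hypothesis. The synopsis can be read as requiring both components, while sections 3 and 7.1 can be read as allowing either. No time point takes precedence.

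Without a rule, neither the false-positive rate nor the power of the primary conclusion is defined. The same six p-values could be called success or failure once they are known. A reader of section 7.2 would also take 90% as the chance that the study reaches its primary conclusion, when it is the chance that one unspecified test is significant.

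**Working it through.** **Inputs.** From section 7.2: mean change 0.5, SD 1.5, n = 97, power 90%, paired t-test. From section 7.1: 2 components × 3 post-dose times = 6 tests, taking one score per component. Alpha and sidedness are not stated. The correlations between tests are not in the protocol and are assumed below. The same mean and SD are used for every test.

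**Reproducing the plan's figure.** Power comes from the noncentral t distribution with noncentrality (0.5/1.5)·√n and n − 1 degrees of freedom.

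- Two-sided 5% (equivalently one-sided 2.5%): 0.8985 at n = 96 and 0.9015 at n = 97, so 97 is the smallest n that reaches 90%.
- One-sided 5%: 90% is already reached at n = 79.
- Two-sided 1%: n = 138 would be needed.

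So 97 and 90% describe one test at two-sided 5%, a level that has to be inferred.

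**Independent tests, n = 97.** Power of one test is 0.9015 at 5% and 0.8410 at 2.5%.

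- Any of six, two-sided false positive: 1 − 0.95⁶ = 0.265.
- Any of six, false improvement: 1 − 0.975⁶ = 0.141.
- All six significant: 0.9015⁶ = 0.537.
- Both components at one time: 0.9015² = 0.813.
- Holm over two components, at least one: 1 − (1 − 0.8410)² = 0.975.
- Holm, a given component: 0.8410 + (0.9015 − 0.8410) × 0.8410 = 0.892.

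**Correlated tests, six at n = 97** (simulation, 60,000 runs; columns are the assumed correlation between times, between components):

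| Quantity | 0, 0 | 0.5, 0.3 | 0.7, 0.5 | 0.8, 0.6 | 0.9, 0.7 |
|---|---|---|---|---|---|
| No true change: any two-sided p < 0.05 | 0.266 | 0.229 | 0.190 | 0.168 | 0.139 |
| No true change: any false improvement | 0.141 | 0.117 | 0.095 | 0.083 | 0.069 |
| True effect: at least one of six | 1.000 | 0.999 | 0.995 | 0.989 | 0.978 |
| True effect: all six | 0.535 | 0.638 | 0.701 | 0.736 | 0.780 |

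**Two components at one time point, n = 97** (simulation, 100,000 runs; columns are the assumed correlation between components):

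| Rule | 0 | 0.3 | 0.5 | 0.8 |
|---|---|---|---|---|
| Both at 5% | 0.812 | 0.824 | 0.836 | 0.857 |
| Holm, at least one | 0.974 | 0.955 | 0.939 | 0.902 |
| Holm, per component | 0.891 | 0.887 | 0.885 | 0.874 |

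**Fewer pairs per component.** Section 2.2 and the screening form (Appendix C) admit people with indigestion, heartburn or both, so 97 treated need not give 97 pairs for each. As an illustration, with correlation 0 to 0.8:

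- 90% have each component (0.9 × 97 ≈ 87 pairs): single-test power 0.867; both required 0.755 to 0.804; Holm at least one 0.960 to 0.882.
- 80% have each component (0.8 × 97 ≈ 78 pairs): 0.828; 0.686 to 0.739; 0.936 to 0.859.

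If people without a component instead stay in with zero change, the result is similar. At 90% the mean is 0.45 and the SD is √(0.9 × (1.5² + 0.5²) − 0.45²) = 1.431, giving power 0.87. At 80% the mean is 0.40 and the SD is √(0.8 × 2.5 − 0.40²) = 1.356, giving 0.82.

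**The case against.** The strongest reply is about weight. The study is one-arm, its data are partly meant to describe performance and inform a two-arm trial, and section 7.3 says the analysis is mainly summaries and graphs. Detail is deferred to a SAP that is not available here and may set a rule. The larger figures come from two extreme rules, any of six and all six, that the protocol never proposes. Under a sensible rule the loss is modest, and with Holm the power for at least one component stays at or above 90%.

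The inputs are also described as very cautious. Repeat episodes may add power, and more than 97 of the 200 enrolled may be treated. With both components required and independent, power would be 91% with 120 treated, 93% with 130, or 93% at n = 97 if the SD were 1.3 (illustrative values). Finally, unaided improvement within an hour could make all six p-values small, and no multiplicity rule corrects that.

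Much of this stands as a limit on the consequence. It does not supply a rule. Section 7.1 describes only the secondary analyses as exploratory, while the primary analysis has a stated hypothesis, p-values and a power claim. The deferral to the SAP is general, and the one sample-size item that section 7.2 assigns to it is the method of re-evaluating the number enrolled. Extra participants would raise power but would not define success. The lack of a control group is a separate limitation that this change would not cure.

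**Conclusion.** The concern holds. The arithmetic in section 7.2 is correct for one two-sided 5% test, but the error rate and power of the primary conclusion are undefined. At n = 97, depending on the reading, the chance of at least one two-sided false positive reaches 14–27% (any of six, unadjusted). Power runs from 54% (all six, independent) to nearly 100% (any of six), with 81–86% for both components at one time point.

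These figures rest on the plan's 0.5 and 1.5 for every test, assumed correlations, one score per component and 97 evaluable pairs per component. If each of the eight symptoms were tested, there would be 8 × 3 = 24 tests. The change should be made. The partly descriptive purpose and the pending SAP keep it from being more serious than that.

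**What to change.** In section 7.1, before data are seen:

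- state a two-sided 5% level;
- name one primary time point (60 minutes, for example) and make the other two supportive;
- define one score per component from the listed symptoms;
- state one success rule, at the sponsor's choice: both components significant at 5% with no adjustment, or either component with Holm.

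In section 7.2, keep 97 and restate the power for the chosen rule. If both are required, it is about 81–86%. With Holm, it is about 87–89% per component and 90–97% for at least one. Say that these figures are conditional on 97 evaluable pairs per component. Align the synopsis and section 3, and carry the same rule into the SAP.

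The edits are to text only and need no extra participants or data, although the component score and the time point are real decisions for the sponsor. The downside is a lower stated power if both components are required. Keeping 90% under that rule would take up to about 119 pairs per component (independent components: 0.9502² = 0.903).
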